5.4.3 Other Efficacy Analyses

Best overall response will be summarized and ORR will be provided for each disease histology.

Best response (including CR+PR) will be summarized for each lesion (target lesion, skin lesion, and peripheral blood lesion).

Waterfall plot of target lesions and mSWAT score for maximum tumor shrinkage as a percent change of target lesions will be provided. Also, percent change from baseline over time will be presented using spider plot.

5.5 Pharmacokinetic, Pharmacodynamic, Pharmacogenomic, and Other Biomarker Analyses

5.5.1 Pharmacokinetic Analyses

The Safety Analysis Set will be used for individual E7777 serum concentrations listings. The PK Analysis Set will be used for the summaries of E7777 serum concentrations and PK parameters.

5.5.1.1 Serum Concentration and its PK Parameter Analysis

<Serum Concentration>

E7777 serum concentrations for non-compartmental analysis will be summarized using summary statistics (n, mean, standard deviation [SD], median, minimum [min] and maximum [max]) by nominal time point.

E7777 serum concentrations will be listed for each subject by actual sampling time.

<PK Parameter>

PK parameters will be derived by non-compartmental analysis using WinNonlin software (version 6.2.1 or later) according to 302-104.01-MNL.

The following pharmacokinetic parameters for E7777 will be calculated: maximum observed concentration (C_{max}) , time at which the highest drug concentration occurs (t_{max}) , area under the concentration-time curve from zero time to time of last quantifiable concentration $(AUC_{(0-t)})$, area under the concentration-time curve from zero time extrapolated to infinite time $(AUC_{(0-inf)})$, terminal elimination phase half-life $(t_{1/2})$, total clearance (CL), volume of distribution at terminal phase (V_z) , volume of distribution at steady state (V_{ss}) , accumulation index (R_{ac}) of C_{max} $(R_{ac}(C_{max}))$, $R_{ac}(AUC)$.

Other PK parameters may be calculated as appropriate.

Summary statistics will be tabulated for the PK parameters of E7777. Summary statistics (n, mean, SD, median, min, and max) will be presented for all parameters (apart from t_{max} where mean and SD are not required). In addition, geometric mean and coefficient of variation (CV) will also be presented for all parameters apart from t_{max} .

PK parameters of E7777 for each subject will be listed.

5.5.1.2 Pharmacokinetic Data Figures

The linear and semi-log plots of E7777 serum concentration versus actual time will be displayed by individual subjects. The actual time will be plotted on the X axis and the concentrations of E7777 will be plotted on the Y axis.

The linear and semi-log mean (+SD) plots of E7777 serum concentration versus nominal time will be displayed. The nominal time will be plotted on the X axis and the mean (+SD) will be plotted on the Y axis on the same graph by visit (Day 1 of Cycle 1, 3 and 5).

5.5.2 Pharmacodynamic, Pharmacogenomic, and Other Biomarker Analyses

Immunogenicity:

The measurement value will be listed for anti-E7777 antibody, anti-IL-2 antibody and neutralizing activity of anti-E7777 antibody in safety analysis set.

If antibody production is observed, the frequency and percentage of all antibody and neutralization activity will be calculated by visit. Titers of antibody will be summarized using summary statistics (n, mean, SD, median, min and max) by visit.

The semi-log mean plots of titer of antibody (anti-E7777 antibody and anti-IL-2 antibody) versus nominal time will be displayed. The nominal time will be plotted on the X axis and the mean will be plotted on the Y axis on the same graph.

Pharmacodynamics:

PD analysis will be performed on the PD analysis set. The measurement value (and the change from baseline, if necessary) of sIL-2R, LDH and T-cell subsets (CD4+, CD4+/CD25+, CD4+/CD25+/Foxp3+, *CD4+/CD7-, *CD4+/CD26-) (*Only for mycosis fungoides and Sézary syndrome) for each evaluation period will be summarized using the number of subjects, mean, SD,

median, minimum and maximum for each disease and overall. In addition, mean plot of recorded values over time will be created.

5.6 Safety Analyses

All safety analyses will be performed on the safety analysis set. All safety result will be summarized for each disease and overall. Safety variables include AEs, clinical laboratory parameters, vital signs, weight, ECOG PS, 12-lead ECGs results, and ophthalmologic test results.

5.6.1 Extent of Exposure

Number of cycles received, duration of treatment, total number of doses, total doses (overall/ by cycle) and relative dose intensity will be summarized. Number and percentage of subject with each starting dose will be provided by cycle.

5.6.2 Adverse Events

The AE verbatim descriptions (investigator terms from the CRF) will be classified into standardized medical terminology using the Medical Dictionary for Regulatory Activities (MedDRA). AEs will be coded to the MedDRA (Version 19.1 or higher) lower level term (LLT) closest to the verbatim term. The linked MedDRA preferred term (PT) and primary system organ class (SOC) will also be captured in the database.

A treatment-emergent adverse event (TEAE) is defined as an AE that emerged on or after the date of first dose of study drug, having been absent at pretreatment (Baseline) or

• Reemerged during treatment, having been present at pretreatment (Baseline) but stopped before treatment, or

• Worsened in severity during treatment relative to the pretreatment state, when the AE was continuous.

Only those AEs that are treatment emergent will be included in summary tables. All AEs, treatment emergent or otherwise, will be presented in subject data listings.

Over view of TEAEs and treatment-related TEAEs include the number and percentage of subjects with any TEAEs, treatment-related TEAE, TEAEs with grade 3 or higher, serious TEAEs (death, other SAEs) and TEAEs leading to study drug dose adjusment (study drug withdrawal, dose reduction, interruption).

The number and percentage of subjects with TEAEs will be calculated from the following viewpoints.

- All/Treatment-related TEAEs by PT
- All/Treatment-related TEAEs by SOC/PT
- All/Treatment-related TEAEs with Grade 3 or Higher by PT
- All/Treatment-related TEAEs with Grade 3 or Higher by SOC/PT
- All/Treatment-related TEAEs by SOC/PT and Grade
- All/Treatment-related TEAEs with Grade 3 or Higher by SOC/PT and Grade
- All/Treatment-related Serious TEAEs by PT
- All/Treatment-related Serious TEAEs by SOC/PT
- All/Treatment-related Serious TEAEs by SOC/PT and Grade

- All/Treatment-related TEAEs leading to withdrawal by SOC/PT
- All/Treatment-related TEAEs leading to dose reduction by SOC/PT
- All/Treatment-related TEAEs leading to dose interruption by SOC/PT
- All/Treatment-related TEAEs leading to delay by SOC/PT
- Specially grouped TEAE by SOC and PT
- Specially grouped TEAE by SOC and PT and Cycle
- Specially grouped TEAE with Grade 3 or Higher by SOC and PT
- Specially grouped TEAE with Grade 3 or Higher by SOC and PT and Cycle

Where Specially grouped TEAE includes Infusion reactuion, Capillary leak syndrome and related events, Vision disorders, Hepatobiliary disorders, Hematotoxicity, Infection, Skin disorders, Rhabdomyolysis and related events.

In addition, the number and percentage of subjects with TEAEs of infision reaction will be summarized as follows.

- TEAEs of Infusion reaction by SOC/PT and visit
- Time to onset for initial TEAEs of infusion reaction
- Time to onset for initial TEAEs of infusion reaction and visit
- Time to recovery for TEAEs of infusion reaction
- Time to recovery for TEAEs of infusion reaction and visit

In counting numbers of subjects by severity, each subject will be counted only once for that categories. If a subject experienced relevant TEAEs more than once, the subject will be categorized according to the prioritizations of ("Grade 5" > "Grade 4" > "Grade 3" > "Grade 2" > "Grade 1").

Number of TEAEs and TEAE with grade 3 or higher devided by number of patients treated will be calculated per cycle and presented in figures.

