3.2 Overall Study Design and Plan

This is a multicenter, single-arm, open label, Phase 2 to evaluate efficacy, safety, PK and immunogenicity of E7777 in patients with relapsed or refractory PTCL and CTCL. This study composed of the following 3 periods: preparation, treatment and follow-up periods. The preparation period consists of the following four procedures: informed consent (IC), screening, enrollment, and baseline assessment. Informed consent (IC) is able to obtain 28 days before the treatment. Enroll the patient who meet the inclusion criteria and does not meet the exclusion criteria. Conduct the baseline assessment within 7 days before the treatment. Confirm that the patient continue to meet the inclusion criteria and does not meet the exclusion criteria before moving to the treatment period. The

treatment period consists of 1 cycle of 3 weeks and lasts until meet the "discontinuation criteria" or Day 21 of Cycle 8. The evaluation at discontinuation will be performed within 7 days after termination of study treatment.

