7 CHANGES IN THE PLANNED ANALYSES

The list below includes both change from protocol and SAP version 1.0.

- Summarization of "Analysis Sets" has been added (section 5.2.1).
- Summarization of "Completion and discontinuation for treatment" has been deleted because the data is not collected (section 5.2.2).
- Summarization of "CCR4 category", "each disease histology and each stage" and "Relapsed/Refractory status" has been added (section 5.2.3).
- Summarization of "Number of previous systemic chemotherapy regimen" and "each previous systemic chemotherapy" has been added (section 5.2.4).
- Summarization of "prior medication" and "concomitant medication" has been deleted (section 5.2.4).
- Definition of concomitant medication has been changed (section 5.2.4).
- Summarization of "Treatment Compliance" has been added (section 5.2.5).
- Subgroup analyses for efficacy and safety have been added (section 5.3.4).
- Summarization of efficacy endpoints by investigator has been added (section 5.4).
- Handling rule of tumor assessment data has been clarified (section 5.4).
- Summarization of "BOR and ORR focused on PTCL/CTCL evaluation criteris" has been added (section 5.4.1).
- Summarization of "Event/censor" for PFS, DOR and OS has been added (section 5.4.2).
- Kaplan-Meier curve for PFS, OS and OS has been added (section 5.4.2).
- Censoring rule for PFS and DOR has been changed (section 5.4.2).
- Summarization of TTR has been changed to not use Kaplan-Meier method because there is no need to use Kaplan-Meier method if the target is responder. (section 5.4.2).
- Summarization of "Best overall response" has been added (section 5.4.2).

- Summarization of "Best overall response and ORR for each disease histology" has been added (section 5.4.3).
- Summarization of "Best response for each lesion" has been added (section 5.4.3).
- Waterfall plot of "target lesions and mSWAT score" has been added (section 5.4.3).
- Spider plot of "target lesions and mSWAT score" has been added (section 5.4.3).
- Plotting individual values of immunogenity titer and PD markers on mean plot has been deleted (section 5.5.2).
- Summarization of "dose ratio" has been changed to "relative dose intensity" (section 5.6.1).
- Definition of TEAEs has been changed to be conservative (section 5.6.1).
- Detailed listing of AE tables has been added (section 5.6.2).
- Some patterns of summazation on TEAEs has been added (section 5.6.2).

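### Does the TEAE definition leave out baseline conditions that return or worsen after treatment ends?

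*SAP*

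**What the plan says.** SAP Section 5.6.2 gives three routes to the treatment-emergent flag:

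- A new event, absent at baseline, is "defined as an AE that emerged on or after the date of first dose of study drug". No end date is stated.
- A baseline event that had stopped qualifies under "Reemerged during treatment, having been present at pretreatment (Baseline) but stopped before treatment, or".
- A continuing baseline event qualifies if it "Worsened in severity during treatment relative to the pretreatment state, when the AE was continuous".

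The flag controls the tables: "Only those AEs that are treatment emergent will be included in summary tables". All events, flagged or not, go into the subject listings.

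On timing, Section 3.2 states: "This study composed of the following 3 periods: preparation, treatment and follow-up periods". Treatment runs in 3-week cycles until the discontinuation criteria are met or Day 21 of Cycle 8 is reached. The same section adds: "The evaluation at discontinuation will be performed within 7 days after termination of study treatment". Section 7 records that the TEAE definition was altered with a conservative aim. It points to Section 5.6.1, although the definition stands in 5.6.2; that is a clerical slip. Section 9 leaves the derivation rules to separate documents.

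**The concern.** One definition uses two time expressions. The first limb starts at first dose and has no stated end. The second and third say *during treatment*, which the SAP does not define. Section 3.2 separates treatment from follow-up and provides for an evaluation shortly after treatment stops, so the plan itself expects some observation after treatment.

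If *during treatment* were taken to stop when treatment stops, a continuing baseline condition that first worsened afterwards would fail the first limb (it was not absent at baseline) and the third (it was not during treatment). It would then appear only in listings, whatever its grade or seriousness, while a new event on the same day would be tabulated. Safety is a secondary objective, and the flag governs every TEAE table, including those for Grade 3 or higher and for serious events. Two programmers working from this text alone could set the flag differently.

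**Working it through.** The SAP gives no figure on this point, so there is none to reproduce. The check is to run each kind of event through the definition under both readings, then ask which reading the text supports.

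**Step 1. Consequence of each reading, for an event starting after treatment has ended but within the collection period**

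| Event | *During treatment* = after treatment start | *During treatment* = until treatment ends |
|---|---|---|
| New, absent at baseline | TEAE, tabulated | TEAE, tabulated |
| At baseline, stopped, then returned | TEAE, tabulated | Listed only |
| Continuing at baseline, then worsened | TEAE, tabulated | Listed only |

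For events between first dose and the end of treatment, both readings give the same flag. The whole question lies in the last two rows of the right-hand column.

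**Step 2. Which reading the text supports**

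- The second limb contrasts return during treatment with having "stopped" beforehand, in the sense of before treatment began. The same noun in the same bullet then most naturally marks the time after that start.
- The third limb compares severity with the pretreatment state. The contrast is again before against after the start, not on treatment against follow-up.
- When the SAP means the defined interval it says *treatment period*: in Section 3.2, and in Section 5.6.5 for the QTc categories. Section 5.6.2 does not use that term.

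**Step 3. Whether Section 7 shows a conflict**

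The change log states a conservative aim but not which part of the definition changed or in what respect. The change could lie wholly in the first limb. If the stated aim bears on the matter at all, it favours the inclusive reading.

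**Step 4. Whether the evaluation at discontinuation proves a loss**

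Section 3.2 describes that evaluation together with the treatment period and does not assign it to follow-up. A worsening found there may also have begun earlier, since the date of detection is not the date of onset. Its 7-day limit bounds a visit; it gives no number of events.

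**Step 5. What other outputs would show**

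Laboratory worsening is counted as a TEMAV from any post-baseline value (Section 5.6.3). Ophthalmologic results are cross-tabulated against the worst post-baseline result, and ECOG PS against each scheduled visit (Section 5.6.6). These do not replace TEAE tables, but they would still show some worsening of baseline conditions.

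**The case for a change.** The best case for a change is this. The SAP writes the definition out in full and lists it among its changes, so Section 5.6.2 is the operative rule and ought to be clear by itself. The protocol may say how long events are collected, but that does not settle whether *during treatment* ends with treatment. Some of the specially grouped events, such as hematotoxicity, infection and skin disorders, can already be present at baseline in these lymphomas, so the affected rows are not empty in principle. A strict reading would also let a post-treatment laboratory worsening be a TEMAV without being a TEAE. Aligning the three limbs would cost one sentence.

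Part of this stands: the phrase is undefined, the limbs are worded unevenly, and the strict reading is possible. What does not stand is the step from there to a wrong result. The strict reading is the less natural one, and nothing in the SAP shows that it will be programmed. Section 9 places derivation rules in separate documents, where an analyst would settle this phrase along with the collection period. The lack of an end date is something a SAP commonly leaves to the protocol, and it applies to the first limb just as much.

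**Conclusion.** No change to the plan is needed. This is an undefined phrase that analysts can be expected to resolve sensibly: re-emerged and worsened events start at first dose, as new events do, and all three end with the protocol's adverse event collection period. On that reading the effect on TEAE counts is nil.

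The conclusion rests on two assumptions. The first is that *during treatment* means after treatment start, which the surrounding wording supports but does not state. The second is that the separate derivation documents follow it; those documents and the protocol are not at hand. If the flag were instead programmed to close when treatment ends, later return or worsening of baseline conditions would drop from the TEAE tables and remain in the listings. The number of such events cannot be estimated from the SAP. Efficacy results are unaffected either way.

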5.6.3 Laboratory Values

Laboratory results will be summarized using Système International (SI) units, as appropriate.

For all quantitative parameters listed in protocol Section 9.5.1.5.4 Safety Assessments (Laboratory Measurements), the actual value and the change from baseline to each post baseline visit and final observation will be summarized by visit using descriptive statistics. Qualitative parameters listed in protocol Section 9.5.1.5.4 will be summarized using frequencies (number and percentage of subjects), and changes from baseline to each post baseline visit and final observation will be reported using shift tables. Percentages will be based on the number of subjects with both non-missing baseline and relevant post baseline results.

CTCAE ver.4.03 will be used to identify subjects with treatment-emergent markedly abnormal laboratory values (TEMAVs). TEMAV is defined as a post baseline value with an increase from baseline to a grade of 2 or higher. When displaying the incidence of TEMAVs, each subject will be counted once in the laboratory parameter high and in the laboratory parameter low categories, as applicable.

The measured values for quantitative data will be displayed over time using Box plot.

5.6.4 Vital Signs

Descriptive statistics for vital signs parameters (diastolic and systolic blood pressure, pulse rate, body temperature and weight) and changes from baseline will be presented by visit. The measured values will be displayed over time using Box plot.

5.6.5 12-lead ECGs

ECG assessments were performed at each visit. Descriptive statistics for ECG parameters and changes from baseline will be presented by visit. Shift tables will present changes from baseline in ECG interpretation (categorized as normal; abnormal, not clinically significant; and abnormal, clinically significant) by visit. In addition, the number (percentage) of subjects with at least 1 post baseline abnormal ECG result QTc Fridericia during the treatment period will be summarized. Clinically abnormal ECG results in QTc Fridericia will be categorized as follows:

Absolute QTc interval prolongation:

- QTc interval >450 ms
- QTc interval >480 ms
- QTc interval >500 ms

Change from baseline in QTc interval:

- QTc interval increases from baseline >30 ms
- QTc interval increases from baseline >60 ms

5.6.6 Other Safety Analyses

ECOG PS :

The number and percentage of subjects included in each category will be cross tabulated based on baseline and each scheduled visit.

Ophthalmologic test :

The eye test result will be cross tabulated based on baseline and worst post-baseline.

5.7 Exploratory Analyses

Exploratory analyses may be conducted as appropriate. Any exploratory analyses that are performed will be appropriate titled and labeled as exploratory and will be clearly distinguished from planned analyses when results are reported in the Clinical Study Report.

6 INTERIM ANALYSES

No interim analyses are planned for this study.

7 CHANGES IN THE PLANNED ANALYSES

The list below includes both change from protocol and SAP version 1.0.

- Summarization of "Analysis Sets" has been added (section 5.2.1).
- Summarization of "Completion and discontinuation for treatment" has been deleted because the data is not collected (section 5.2.2).
- Summarization of "CCR4 category", "each disease histology and each stage" and "Relapsed/Refractory status" has been added (section 5.2.3).
- Summarization of "Number of previous systemic chemotherapy regimen" and "each previous systemic chemotherapy" has been added (section 5.2.4).
- Summarization of "prior medication" and "concomitant medication" has been deleted (section 5.2.4).
- Definition of concomitant medication has been changed (section 5.2.4).
- Summarization of "Treatment Compliance" has been added (section 5.2.5).
- Subgroup analyses for efficacy and safety have been added (section 5.3.4).
- Summarization of efficacy endpoints by investigator has been added (section 5.4).
- Handling rule of tumor assessment data has been clarified (section 5.4).
- Summarization of "BOR and ORR focused on PTCL/CTCL evaluation criteris" has been added (section 5.4.1).
- Summarization of "Event/censor" for PFS, DOR and OS has been added (section 5.4.2).
- Kaplan-Meier curve for PFS, OS and OS has been added (section 5.4.2).
- Censoring rule for PFS and DOR has been changed (section 5.4.2).
- Summarization of TTR has been changed to not use Kaplan-Meier method because there is no need to use Kaplan-Meier method if the target is responder. (section 5.4.2).
- Summarization of "Best overall response" has been added (section 5.4.2).

- Summarization of "Best overall response and ORR for each disease histology" has been added (section 5.4.3).
- Summarization of "Best response for each lesion" has been added (section 5.4.3).
- Waterfall plot of "target lesions and mSWAT score" has been added (section 5.4.3).
- Spider plot of "target lesions and mSWAT score" has been added (section 5.4.3).
- Plotting individual values of immunogenity titer and PD markers on mean plot has been deleted (section 5.5.2).
- Summarization of "dose ratio" has been changed to "relative dose intensity" (section 5.6.1).
- Definition of TEAEs has been changed to be conservative (section 5.6.1).
- Detailed listing of AE tables has been added (section 5.6.2).
- Some patterns of summazation on TEAEs has been added (section 5.6.2).
- Summarization of "Specially grouped TEAE" has been defined and added (section 5.6.2).
- Summarizations of "time to onset/recovery of infusion reaction" has been added (section 5.6.2).
- Summarization of "number of adverse events per subject" has been added (section 5.6.2).
- Boxplot of measured laboratory parameter values over time has been added (section 5.6.3).
- Boxplot of measured vital sign parameter values over time has been added (section 5.6.4).
- Summarization of "Ophthalmologic test" has been added (section 5.6.6).
- PK parameters have been added(section 8.2.5)
- CTCAE grading rules have been updated (section 13.1)

